initiate, cessation, reducing smoking urges, forgoing cigarettes, and reducing cigarette purchasing behaviors.^{22–26} However, little is known about the impact of cigarillo warnings on behavior.²⁷

In our previous work (R03CA206487, PI [name]) we developed pictorial cigarillo warnings by pairing images with the six FDA text-only cigar warning statements. In an online study with a nationally representative sample, we found that pictorial warnings were more effective at eliciting negative emotional reactions than text-only warnings among young adult cigarillo users and susceptible nonusers. They were also perceived as more effective at discouraging future cigarillo use. We now seek to understand the impact of cigarillo warnings on behavior and intentions at the point-of purchase and after repeated exposure. The presence of warnings that communicate about risk can result in negative emotional reactions and cognitions about the harms of smoking, which may deter purchase. Warnings are also effective after multiple exposures over time through message repetition.²⁸

A behavioral economics framework can model the impact of implementing a cigarillo warnings policy on consumer purchasing behavior in the context of a complex tobacco product marketplace. Behavioral economics frames potential policy measures as ways to decrease the value of a tobacco product for an individual.^{29,30} In this framework, warning labels may work to reduce the value of a product. Value is often measured as demand, or consumption of a product at increasing prices. In behavioral economics, changes in price are considered to be analogous to *changes in effort required* to obtain the product, which indicates value for that individual. There has been a recent call to use a behavioral economics framework for communications research in tobacco regulatory science and apply it to products other than cigarettes.³¹ The Experimental Tobacco Marketplace (ETM) task examines the effects of regulations on tobacco purchasing in the context of a complex tobacco marketplace.⁵² Instead of ‘switching’ from one product to another, participants can choose a mix of tobacco products from an online store. In a typical ETM, across multiple task (i.e., shopping trips) trials, the price of the preferred tobacco product (cigarillos in this study) increases and those of other tobacco products remain constant.^{53,54} Increasing price across shopping trips measures effort required to obtain the product (product demand), and substitution with other products.

The proposed study will contribute to the evidence base needed to support the rulemaking process and will have a significant public health impact. The FDA’s CTP has an interest in effectively communicating the risks of tobacco products, including cigarillos. However, there is a critical gap in the science on how to inform the public of the risks of cigarillo use. This project aims to address the gap in the knowledge about cigarillo risk communication by providing information on best practices for cigarillo warnings. Identifying effective cigarillo warnings is important to inform policy and guide research on effectively communicating risk to ultimately decrease use and tobacco-related morbidity and mortality.

Objective(s)

This Experimental Tobacco Marketplace online survey experiment aims to determine the impact of cigarillo warning format on hypothetical purchasing behaviors.

Methods and Measures

Design

We will conduct a three-group, between-subjects experiment to compare varying cigarillo warning formats: Surgeon General text-only, FDA-proposed text-only, and our developed pictorial cigarillo warning labels. This will be a single survey study.

Setting

Survey participants will complete the online survey in a location of their choosing.

Subjects Selection Criteria

Participants will be recruited by Kantar, a leading data and consulting company with access to 21 million respondents in the United States. Kantar has participated in survey programming and data collection for various social science and public health studies, including tobacco. They will recruit a total of 1,575 cigarillo users, including oversampling Black/African American cigarillo users, with an estimated total of 635 Black/African American and 647 White cigarillo users

Inclusion Criteria

- Age 21-35
- Current cigarillo users: used cigarillos at least one time per week in the past month
- Members of the Kantar Media panel

Exclusion Criteria

- Non-English speakers
- Non-current cigarillo users
- Not members of Kantar Media

Sample Size

- We estimate 1575 participants will be eligible to complete the survey.

Interventions and Interactions

Kantar will contact individuals to participate, who will complete an eligibility screener. Eligible participants will first complete measures of demographics and tobacco use behaviors. Next, participants will be randomized to one of three experimental conditions to complete six purchasing tasks (i.e., mock shopping trips). Participants will indicate their preferred brand and flavor of cigarillos.³² If their preferred brand of cigarillo is not one of the top four brands, we will ask them to select one of the available brands. The experimental stimuli will be placed on that branded packaging.

We will ask participants the average amount of money they spend each week on tobacco products; they will receive that balance for each mock (i.e., hypothetical) shopping trip, as is standard for ETM studies.³³ We will ask participants to imagine they were shopping in a convenience store, and to view six items available for purchase: preferred cigarillo brand, cigarette product (menthol and non-menthol), e-cigarette product (three variations), oral nicotine pouches, non-alcoholic drink, and snack food. They will be instructed to make hypothetical purchases of tobacco products that they would use for the week. In each shopping trip, the price of cigarillos will increase while those of alternative products remain the same. In each trial, participants can choose any combination of tobacco and non-tobacco products to ‘buy’, as long as they stay within their experimental budget. Across six mock shopping trips, the price of one of their preferred cigarillo products will increase from \$0.25, 0.50, \$0.75, \$1.50, \$3.00, \$6.00, based on an average price of \$0.91 per cigarillo.³⁴ Cigarette price will remain constant at \$6.00 per pack (\$0.30 per cigarette), e-cigarettes will be priced at \$4 per e-liquid pod or \$6 for 30 ml e-

liquid or \$12 for disposable device, and oral nicotine will be priced at \$4.00. Food and drink will be priced at \$2 each. Cigarillos will be purchased as singles to generate demand curves (see Measures and Analysis Plan).. This models other ETM studies.³³

After completing the hypothetical purchase tasks, we will assess additional constructs from our conceptual model. First, we will assess cigarillo warning label recognition (a measure of attention). We will then show the cigarillo warning to participants from their assigned experimental condition and ask them to respond to items assessing negative affect, thinking about the warnings, and intentions to quit using cigarillos.

At the end of this experiment, participants will view a **debriefing** page, including an explanation of the purpose of the study, emphasizing that the study is not promoting the use of cigarillos or any tobacco product and will include links to cessation services and information about the harms of cigarillo use. Participants will be compensated with 100 points (~\$2 value) by Kantar. These points can be used in exchange for a variety of items, including gift cards. We will not collect any identifying information such as name or birthdate.

Outcome Measure

The average total number of cigarillos purchased is the primary outcome.

We will assess secondary outcomes: average total amount (mg) of combusted and non-combusted tobacco purchased in the ETM.

In secondary analyses, we will also generate demand indices for cigarillos, including: demand intensity (consumption at the lowest cigarillo cost), demand elasticity (rate of change in demand for cigarillos), price of cigarillos resulting in maximum purchasing, the amount of money spent at the maximum purchasing price.

In exploratory analyses, we will assess cross-price elasticity measures, negative affect, cognitive elaboration (thinking about the warnings), intentions to quit using cigarillos, perceived message effectiveness, and warning recall/recognition, which is a measure of attention.

We will also measure several **covariates**: use of other tobacco products, cigarillo dependence, sexual orientation, race/ethnicity, socioeconomic status, sex, gender identity, and age.

Analytic Plan

This study will examine the impact of cigarillo warnings on purchasing behavior in a hypothetical shopping task using the online Experimental Tobacco Marketplace. The primary outcome is the average total amount of cigarillos “purchased” (hypothetical shopping task) compared across study conditions.

Baseline differences between participants (e.g., sex) across warning conditions will be examined using t-tests for continuous variables and χ^2 tests for categorical variables to evaluate randomization balance. The primary outcome, average total number of cigarillos purchased, will be modeled using random-effects linear regression models to account for the within-person correlation among the repeated measures represented by the six purchasing tasks. Warning condition will be included as a between-subjects fixed effect. Models will control for any variables that differ at baseline between conditions. We will also assess whether Black/African-American race moderates the effect of warning condition by including interaction terms between Black/African American race and warning condition. These same analyses will also be

conducted for our secondary outcomes for average total of mg combusted and non-combusted tobacco products.

In secondary analyses, demand curves will be generated for each cigarillo warning condition in each of the ETM conditions using the exponential demand equation, $Q = Q_0 * 10^k(e^{-\alpha Q_0 C} - 1)$, where Q is the mg of nicotine purchased at a given price, Q_0 is peak demand consumption or intensity (typically occurring at the lowest price), k is a constant across all compared conditions, and alpha (α) is the rate of change in demand or elasticity.³⁵ To determine the extent to which pictorial warnings decrease cigarillo purchasing relative to the text-only warning conditions, the global fits of the demand curves for cigarillos from each condition will be compared using an extra-sum-of-squares F-test, which compares whether the fitted parameters (specifically, Q_0 and α) are significantly different across each curve. A significant difference in α would represent a difference in the essential value of the product, while a difference in Q_0 would indicate that purchasing was reduced in absolute terms but the underlying 'value' of the product was unchanged.^{36,37} Finally, each individual demand index will be compared across conditions using t-tests to determine if pictorial warnings affected specific indices of demand differentially. The number of cigarillos purchased is higher for text-only warnings compared to pictorial warnings at the same price, but demand overall will decrease as price increases.

Exploratory analyses will examine the effects of warning condition on other constructs in the conceptual model including negative affect, cognitive elaboration, behavioral intentions, and warning recall/recognition. Because these outcomes are measured only once after the completion of all six purchasing tasks, continuous outcomes will be modeled using standard linear regression modeling and categorical outcomes will be modeled using logistic and multinomial regression. All tests will be two-sided with a 0.05 significance level.

In exploratory analyses, to determine the extent to which each alternative product substituted for cigarillos, cross-price elasticities will be calculated as the slope of the regression line (B_1) fit to the log-transformed mean purchasing in mg of nicotine for each alternative tobacco product when offered at fixed prices (C) versus log-transformed cigarillo price (P): $\log C = B_0 + B_1 \log P$. Positive values indicate product substitution. We will use PRISM GraphPad Version 8.1.1 to generate the behavioral economics indices, demand curves, and cross-price elasticities. We will be able to determine if viewing a pictorial warning on a cigarillo resulted in substitution with another tobacco product without a pictorial warning, such as cigarettes or e-cigarettes, or a non-tobacco product, such as food or drink.

Every effort will be made to minimize the presence of missing data. Analyses will use all available data. Since missing data in a single item of a multi-item scale leads to a missing total, we will consider imputing both at the level of the item and scale total. Additionally, to evaluate the generalizability of our results, we will use t-tests and chi-squared tests to examine pairwise differences in characteristics between participants for whom we have complete data and those for whom we do not.

Human Subjects Protection

Subject Recruitment Methods

Kantar works with permission-based panels with 88 million respondents, including 21 million in the United States. Recruitment includes traditional advertising and through internal and external affiliate networks. Kantar uses a diverse set of sources to reduce panel bias. When recruiting participants into studies, Kantar engages in data validation to ensure quality respondents and

responses. Kantar will recruit participants, directly inviting them to participate in the experiment. Potential study participants will complete an eligibility screener for inclusion into the ETM study. Participants must be ages 21-34 and be current cigarillo users (use cigarillos at least one time per week for the past month). Further, because we are studying cigarillo warnings in the U.S., only those living in the U.S. are eligible. Kantar will also oversample for young adult Black/African American cigarillo users. Kantar oversamples by enrolling approximately 20% additional participants to the study.

Informed Consent

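### The random-effects model for the six shopping trips names no price term; this matters only if unfinished sessions are analysed and break-off differs by arm

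*Combined protocol and SAP*

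**What the plan says.** The Analytic Plan chooses a random-effects linear model "to account for the within-person correlation among the repeated measures represented by the six purchasing tasks". The terms it names are warning condition ("Warning condition will be included as a between-subjects fixed effect"), any baseline variables found to differ between conditions, and race-by-condition terms for moderation. The mg outcomes for combusted and non-combusted tobacco are to be analysed in the same way.

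Under Interventions and Interactions, the six repeated measures are six ascending prices: "In each shopping trip, the price of cigarillos will increase while those of alternative products remain the same". The listed prices are $0.25, $0.50, $0.75, $1.50, $3.00 and $6.00. The Analytic Plan expects purchasing to respond: "but demand overall will decrease as price increases". Price enters the separate demand-curve and cross-price analyses, but it is not named in the primary model.

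On incomplete data, the end of the Analytic Plan says "Analyses will use all available data". Imputation is raised only for multi-item scales ("we will consider imputing both at the level of the item and scale total"). A completeness check is planned "to examine pairwise differences in characteristics between participants for whom we have complete data and those for whom we do not". There is no rule for a participant who leaves partway through the trips. The Design section adds: "This will be a single survey study".

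**The concern.** Because the price only rises, anyone who stops early contributes low-price trips and loses high-price ones. A model without price cannot tell a person who bought heavily from a person observed only when cigarillos were cheap. If one arm has more early stoppers, its estimated mean is pulled upward.

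For cigarillos the sign follows break-off. More break-off under pictorial warnings would mask a benefit, and more under a text warning would create or exaggerate one. For non-combusted tobacco the direction is not known in advance, because purchasing may rise as cigarillos become dearer. The planned completeness check compares participants' characteristics, not trips completed by condition, so it need not reveal the problem.

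**Working it through.** The plan gives no break-off rate, effect size or standard deviation, so it has no figure of its own to reproduce.

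**Inputs.** From the documents: the six prices, 1,575 participants, two-sided 0.05 tests, and the demand equation, read with the bracket in the exponent: Q = Q0 × 10^[k(e^(−α·Q0·C) − 1)]. Assumed: equal allocation (1,575/3 = 525 per arm; the ratio is not stated), cigarillo counts that follow this equation (the plan writes it for mg of nicotine), the curve parameters, the between-person spread and the break-off rates.

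**1. Complete data.** Everyone sees the same six prices, so each arm mean is the same six-price average whether or not price is fitted. In simulation the two condition estimates differ by less than 1e-10, and the standard errors agree.

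**2. Closed form.** Suppose a share p of one arm stops after trip n and nobody stops in the other. Let m_n be the mean over the first n prices and w(n) = n/[1 + (n − 1)·ICC]. Then

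shift = p·w(n)·(m_n − m_6) / [p·w(n) + (1 − p)·w(6)].

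Take Q0 = 10, k = 2, α = 0.02:
- Trip means are 7.99, 6.45, 5.27, 3.03, 1.25 and 0.40, so m_3 = 19.71/3 = 6.57 and m_6 = 24.39/6 = 4.065.
- With ICC 0.217, w(3) = 3/1.434 = 2.092 and w(6) = 6/2.085 = 2.878.
- For p = 0.10, n = 3: 0.2092 × 2.505 / (0.2092 + 2.590) = 0.187, or 4.6% of the mean. A REML simulation gave 0.189.
- For p = 0.05: 0.1046 × 2.505 / (0.1046 + 2.734) = 0.092, or 2.3% of the mean.

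**3. Range.** Five curves (mean 1.8 to 8.1 cigarillos per trip), log-SD 0.5 to 1.1 between persons, and stopping after trip 1, 3 or 5 or spread over trips 1 to 5:
- 5-point difference: 0.01 to 0.20 per trip (0.6% to 3.0% of the mean).
- 10-point difference: 0.03 to 0.41 (1.2% to 6.6%).
- Equal 10% break-off, no true effect: zero in closed form. With a proportional effect the contrast grows by 1.2% to 5.9% of its own size.

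**4. Trial size.** A separate simulation used 525 per arm, no true effect, 400 runs, Q0 = 10, α = 0.006 (mean 6.69 per trip), additive errors (SD 4 between persons, 2 within), and random break-off spread evenly before trips 2 to 6:

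| Break-off, arm 1 v arm 2 | Shift, no price | Rejection, no price | Shift, price | Rejection, price |
|---|---|---|---|---|
| 0% v 0% | −0.001 | 3.8% | −0.001 | 3.8% |
| 10% v 10% | 0.013 | 4.2% | 0.015 | 3.8% |
| 5% v 10% | 0.070 | 5.0% | −0.010 | 4.8% |
| 5% v 15% | 0.163 | 9.0% | 0.001 | 3.8% |
| 5% v 25% | 0.319 | 24.2% | −0.010 | 5.8% |

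Simulation error on each shift is about 0.252/√400 = 0.013. Multiplicative errors gave similar shifts without price for the last three rows (0.059, 0.174, 0.338), with rejection of 4.0%, 8.0% and 12.0%.

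Over the five curves of step 3 at log-SD 0.8, with an assumed 15% reduction, power is 60–73% with complete data. Without price it is 51–67% at a 5-point pictorial excess of break-off and 36–62% at 10 points. With price it is 64–72% in both cases.

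**5. Limits of the price term.** When stopping is unrelated to purchasing and there is no true effect, the residual shift is within simulation noise (at most 0.024). With a proportional 15% effect it is −0.035 to −0.003.

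When stopping depends on first-trip purchasing, the result depends on the assumed strength. The following illustrate a single strength (hazard multiplied by exp(±0.7) per SD, 10% v 0%):
- Heavier buyers stop more: 0.045–0.562 without price, 0.017–0.235 with it (36–60% remains).
- Lighter buyers stop more: 0.024–0.307 without price, −0.107 to −0.008 with it (reaching −0.120 with a 15% effect).
- Imputing missed trips within condition from earlier trips: −0.012 to 0.037.

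These are not bounds. A different data generator at the same strength left about 21–70% when heavier buyers stopped more. At exp(1.5), with heavier buyers stopping after trip 1, one case went from 0.030 without price to 0.073 with it. At exp(−1.5), with lighter buyers stopping after trip 3, another went from 0.198 to −0.263.

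**The case against.** The best defence is that silence is not exclusion. The plan does not call condition the only fixed effect, and it models price explicitly in the demand curves. That analysis is secondary and in mg of nicotine, however, so it does not stand in for the primary test. The Analytic Plan lists its model terms and price is not among them.

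The second defence is stronger. This is one online survey run by a panel vendor that validates responses. The all-available-data sentence is followed directly by text on multi-item scales, and nothing says that unfinished sessions reach the dataset. Break-off may be rare or even across arms, and at a 5-point difference the simulated false-positive rate stayed nominal. All of this stands, and it limits the weight of the point.

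Three stronger readings are tempting, and none is supported:
- **That the planned contrast is biased as written.** This needs unfinished sessions in the analysis and unequal break-off, and the documents show neither.
- **That a price term fully protects the contrast.** Step 5 shows that it can leave much of the bias, reverse it or enlarge it when stopping depends on purchasing.
- **That the mg outcomes share the same size of bias.** No mg calculation was made, and the direction for non-combusted tobacco is unknown.

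**Conclusion.** The omission is in the text; the harm is conditional. With six complete trips, or equal break-off, leaving price out does not materially change the condition contrast. If unfinished sessions are kept and break-off differs by arm, the arm with more break-off appears to buy more: about 0.01 to 0.2 cigarillos per trip at 5 points, which is small, and 0.03 to 0.4 at 10 points. These figures rest on assumed demand curves, spread and stopping patterns, not on anything the plan reports. Confidence is high that the term is not named and moderate that it will matter. The change is worth making before analysis because it is nearly free and also settles how unfinished trips are handled.

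**What to change.** - Add price as a six-level within-person fixed effect to the primary model. The fixed order makes price and trip number the same factor, so one term serves for both. Add it to the mg models for consistency.
- Keep the condition difference averaged over the six prices as the primary contrast.
- State whether unfinished sessions are in the analysis set, and report the number of trips completed by condition.
- If break-off is not negligible, add a sensitivity analysis that imputes missed trips within condition from the trips already made. In the illustrations stopping depended on observed first-trip purchasing, which favours this method, so it should be read as a check and not a guarantee.

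Cost: a few sentences in the Analytic Plan and 6 − 1 = 5 degrees of freedom out of up to 1,575 × 6 = 9,450 observations. No new data are needed, and the contrast does not change if all trips are complete.

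### Covariates are chosen by baseline significance tests, so weekly tobacco spend, which sets every participant's purchasing budget, would enter the model only by chance, if at all

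*Combined protocol and SAP*

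**What the plan says.** The Analytic Plan begins with balance testing: "Baseline differences between participants (e.g., sex) across warning conditions will be examined using t-tests for continuous variables", and chi-squared tests for categorical ones. For the primary random-effects model it then says: "Models will control for any variables that differ at baseline between conditions". The same analyses are to be "conducted for our secondary outcomes for average total of mg combusted and non-combusted tobacco products". All tests are two-sided at 0.05. No covariate is fixed in advance for the comparison of conditions.

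The Outcome Measure section names eight covariates to be measured: "use of other tobacco products, cigarillo dependence, sexual orientation, race/ethnicity, socioeconomic status, sex, gender identity, and age". It gives them no stated role in the model.

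On the budget, Interventions and Interactions says: "We will ask participants the average amount of money they spend each week on tobacco products; they will receive that balance for each mock" shopping trip. Participants may buy any mix of products "as long as they stay within their experimental budget". Weekly spend is in neither the covariate list nor any part of the analysis text.

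On timing, the same section says: "Eligible participants will first complete measures of demographics and tobacco use behaviors", and then: "Next, participants will be randomized to one of three experimental conditions to complete six purchasing tasks". The spend question is described after that second sentence.

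**The concern.** Conditions are assigned at random, so a baseline difference is chance by construction. Its p-value carries no information on whether the variable predicts how many cigarillos are bought. The rule therefore admits some variables at random, whether or not they matter, and usually leaves out a prognostic variable that happens to look balanced. What the primary model contains is unknown until the data are in.

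The rule is also incomplete for continuous variables. A t-test compares two groups and there are three conditions, so the plan does not define when such a variable differs. One chi-squared test does cover three groups for categorical variables.

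Weekly spend shows the problem best. At price p, a participant cannot buy more than spend / p cigarillos, so the design itself ties this variable to the outcome. How strongly is unknown, because the budget covers all products and the cap matters only where it binds.

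At stake is precision in the main contrasts and in the race-by-condition interaction, which starts from a larger standard error.

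**Working it through.** The documents state no power, SD, R² or target effect, so there is no figure of the plan's to reproduce.

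**Inputs from the documents.** Three conditions; 1,575 participants, of whom an estimated 635 are Black/African American; two-sided 0.05; eight listed covariates.

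**Assumptions.** Allocation 1:1:1, hence 1,575 / 3 = 525 per arm. Illustrative effect of 0.15 SD between two arms. R² is the share of between-participant variance in average purchases that the covariates explain.

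**1. Chance that a randomised variable is flagged.**
- One three-group test: 5.0%.
- Any of three pairwise t-tests: P(q > 1.96·√2), with q the studentised range for 3 groups and 1,572 df, = 12.3% (simulation 12.2%).
- Spend, if only the eight listed variables are tested: 0%.

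**2. Chance that at least one of the eight listed covariates is flagged** (independence assumed).
- One test each: 1 − 0.95⁸ = 34%.
- Pairwise t-tests for two continuous covariates: 1 − 0.95⁶ × 0.878² = 43%.
- Pairwise t-tests for three: 1 − 0.95⁵ × 0.878³ = 48%.

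**3. Power for 0.15 SD.** With a fixed covariate set, noncentrality = 0.15 / √((1 − R²) × 2/525) with 1,571 df. At R² = 0 this is 0.15 / 0.0617 = 2.43. At R² = 0.25 it is 0.15 / 0.0535 = 2.81. Equivalent unadjusted sample size = 1,575 / (1 − R²). The plan's rule was simulated for one covariate in three arms of 525 (20,000 runs).

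| R² | Fixed set: power | Equivalent N | Plan's rule: power (one test / pairwise) |
|---|---|---|---|
| 0 | 68.0% | 1,575 | – |
| 0.03 | 69.4% | 1,624 | 68.5 / 68.6% |
| 0.10 | 72.6% | 1,750 | 68.2 / 68.6% |
| 0.25 | 80.1% | 2,100 | 68.9 / 69.9% |
| 0.36 | 85.9% | 2,461 | 69.6 / 71.0% |

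Differences of a few tenths of a point in the last column are simulation error.

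**4. Other effect sizes, same formula.** At 0.10 SD, power is 37% unadjusted and 40% at R² 0.10. At 0.20 SD, it is about 90% unadjusted, 92.7% at R² 0.10 and 96.2% at 0.25. At 0.25 SD, it is already 98% unadjusted.

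**5. Type I error under the plan's rule.** In the same simulation it is 4.4% (one test) and 4.2% (pairwise) at R² 0.25, and 4.3% and 4.0% at R² 0.36. The rule is mildly conservative when the covariate is prognostic.

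**6. How large could R² be for spend alone?** An illustration used the six protocol prices with assumed lognormal spend, exponential demand, and a correlation of 0 to 0.6 between log spend and demand. R² was 0.001 (median budget $60, correlation 0), 0.10 ($30, 0.3) and 0.37 ($15, 0.6). At 0.001 there is no gain.

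**7. Interaction.** The Black/African American share is 635 / 1,575 = 0.403. Spread evenly over arms, the interaction's standard error relative to the main contrast is √(1/0.403 + 1/0.597) = 2.04. The comparator here is all other participants. Using only the estimated 647 White participants gives √(1,575/635 + 1,575/647) = 2.22.

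**The case against.** Randomisation keeps the unadjusted comparison unbiased, and the rule errs on the conservative side, so no false conclusion is being invited. That stands, and it limits the point to precision and prespecification.

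The power figures rest on a chosen effect and an unknown R². A rise from 68% to 80–86% needs both an effect near 0.15 SD and strong covariates. At 0.25 SD there is almost nothing left to gain, and the upper R² for spend requires small budgets and an assumed correlation of 0.6. This also stands, so the figures are illustrative. The data-driven choice of model is a weakness at any R².

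The 5–12% for spend presumes that spend is tested at all. On the narrower reading it never enters, which makes the omission more complete.

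Spend may not be a true baseline variable, because its question is described after the randomisation sentence and the survey appendix is not shown. This is a fair caution and must be settled before spend is used.

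Dependence, other tobacco use and socioeconomic status may partly stand in for spend. They enter by the same chance rule, so they do not repair it. Finally, the 34–48% assumes independent covariates. Sex with gender identity, and race/ethnicity with socioeconomic status, are plausibly associated, so these are nearer to upper values.

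**Conclusion.** The concern holds. The plan lets significance tests on randomised groups decide the adjustment in the primary and secondary mg models, and it leaves out the one variable that limits the outcome by design. The choice of model is data-dependent whatever the covariates explain. The loss of precision is conditional: equivalent to forgoing 175 participants (1,750 − 1,575) at R² 0.10 or 525 (2,100 − 1,575) at R² 0.25, and nothing if the covariates predict little. These figures assume equal allocation. Confidence is high that the rule is inferior to a fixed set, and lower on the size of the gain. The sponsor should change it, but it does not threaten the validity of the comparison.

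**What to change.** - Delete the test-based adjustment sentence and the baseline significance tests. Report baseline characteristics by condition descriptively.
- Name a short prognostic set for the primary and secondary mg models, used whatever the observed balance: weekly tobacco spend, cigarillo dependence, other tobacco use, Black/African American race and age. Add baseline cigarillo use if the survey records it as a quantity.
- Fix the functional form of spend and the handling of zeros beforehand. log(1 + spend) is one option. The cap itself is linear in spend, so an untransformed term is also defensible.
- State when spend is asked. Include it only if it is recorded before assignment, or at least before any warning is shown.
- Report the unadjusted model as a sensitivity analysis.

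The cost is SAP wording, two checks of the survey (timing of the spend question, and whether cigarillo use is quantitative) and a few degrees of freedom out of 1,575 participants. No extra recruitment is needed. The change should be made before outcome data are seen.
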